### Analyses of Secondary Outcomes.

*Dose-response.* We anticipate that there will be a dose-response relationship, with the control arms having the lowest values, high-engagement arms, the highest values, and moderate-engagement arms having values in between. We will construct mixed models to estimate the sizes of these effects, and to determine whether effects are linear or nonlinear in the degree of engagement.

*Subgroup Analyses.* We will conduct a number of analyses aimed at estimating treatment effects within strata of age (younger or older than age 72), gender (male or female), education (greater or less than 14 years), and center (Dallas or Hamburg). We expect each of these strata to comprise roughly half of the subjects, except that our sample will likely be 65% female, reflecting the sex imbalance in the elderly. We will replicate our main analyses in each of the stratum subgroups, and additionally test for interactions.

*Incomplete data.* A major concern in any follow-up study is that there will be substantial dropout, eroding trial power. As indicated above, we expect no more than 15% to 20% of subjects to fail to complete the followup evaluation schedule. This is not a large fraction of dropout, and we have provided for its effects on power in our sample-size calculations. A second concern is that dropouts may differ systematically from completers, potentially introducing bias into estimated treatment contrasts. Our primary approach to analysis is to use mixed models, which give correct results as long as the dropout mechanism is missing at random — i.e., the probability of dropout, given the potentially missing observation and all prior observed data, does not depend on the potentially missing observation. Moreover, as long as the dropout is roughly balanced between treatment arms, it is unlikely to have a substantial biasing effect on estimated treatment effects, even if the dropout mechanism is not missing at random. In any event, if dropout is excessive or is unbalanced between arms, or there is concern that it is not missing at random, we are prepared to conduct analyses for sensitivity to nonignorable (i.e., biasing) dropout using general methods that [name] has developed.

*Latent Factor Modeling.* As a further form of secondary analysis, we will analyze the cognitive outcome variables simultaneously using a latent-variable approach. With this method, one models the several cognitive variables at each measurement time as being statistically independent given an unobserved, subject-specific latent variable. One accommodates serial correlation within subjects by estimating correlation of the latent variable within subjects over time. The approach evaluates treatment and time effects by modeling the mean of the latent variable as a function of the predictors, and each subject's estimated latent trajectory serves as a summary of his outcome status. We will also apply such models to the four-variate fMRI primary outcome.

*Neuroimaging Analyses.* We will test for a Group x Time interaction on the primary measure of modulation capacity. For the large-scale brain network analyses, we will utilize measures of connectivity between major nodes within the networks as indicators to develop constructs for the executive fronto-parietal network, salience network, and default network at each interval of data collection. To measure increases in hippocampal volume, we will segment the left and right hippocampus into four regions of interest (subiculum, CA1 and CA2/CA3/CA4, dentate gyrus, and entorhinal cortex) for all individual high-resolution MRI images. This division into 4 regions of interest (ROI) will ensure sufficient reliability and reproducibility of the subfield distinctions. These ROIs will be entered into the same Group x Time ANOVA as in the fMRI analyses.

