We propose a study that would allow us to evaluate the effectiveness of engagement on cognitive function and determine whether mental effort is a contributing factor to changes in cognitive function. We plan to enroll 90 participants in the Impact of Challenging Engagement study and assign them to one of three groups: high-demand photography, moderate-demand photography, and active placebo. These initial groups will allow us to collect data and address the feasibility for converting the project into a full trial. Participants will engage in their different engagement conditions for 15 hours per week, based on successful results from the initial AIM study. In the Impact of Challenging Engagement study, we expect to expand on the results of the AIM study to determine if high-demand activities result in any observable brain changes when compared to moderate demand or placebo activities. Behavioral and neural measures of cognitive change will be assessed, providing considerable insight into mechanisms of change. Subjects will be characterized thoroughly in terms of behavioral tests of cognitive function, and a subset of subjects who meet neuroimaging criteria will undergo an fMRI procedure.

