### **Concise Summary of Project.**

In the proposed research, we will enroll a total of 90 subjects over 16 weeks. Just as in the original AIM study (approved by UTSW IRB #072010-144), subjects will be randomly assigned to participate in one of 3 conditions with 30 subjects per group. Two of the groups involve active intellectual engagement. In these groups, novice subjects will engage in high-demand or moderate-demand photography in five hours of structured courses with professional instructors for each of the 16 weeks. Subjects will also be required to put in an additional investment of 10 hours each working on a project to which they can apply their learned skills. Subjects are expected to be working on their projects for a total of 210 hours of engagement over the 16 weeks. We will measure pre/post change in multiple measures of cognitive and neural function, affect, and activity over the 16 weeks, and contrast change with one control group. The control group, the Placebo Control, will engage alone at home in tasks that are relatively low in intellectual engagement such as listening to music and radio or completing work-books that rely primarily on activation of knowledge. Preliminary data collected at the University of Illinois has indicated that volunteers willingly engage in a similar program.

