### **Participant Recruitment**

90 subjects will be recruited to participate in this study that lasts 16 weeks. Subjects will participate in one of 3 conditions with 30 subjects per group. Two of the groups involve active intellectual engagement. In these groups, novice subjects will engage in high-demand or moderate-demand photography in five hours of structured courses with professional instructors for each of the intervention weeks. The third group consists of an active placebo group that will engage in cognitively demanding activities at home (like completing crosswords and listening to music).

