### **Intervention (Weeks 3-16)**

Subjects will be pseudo-randomly assigned to intervention groups (based on gender and education criteria and the needs of the study) and then will participate for at most 14 weeks in the manipulation to which they were assigned. All will be told that there are numerous studies in the literature suggesting that the condition to which they were assigned is a form of engagement that has been shown to improve cognition. This is true, as many correlational studies have shown that engagement in tasks as passive as watching television is related to better cognition. All subjects will be required to agree to participate in any of the three conditions so that no condition will be biased. They will be novices at the use of the digital camera and will have had only minimal experience with computers, , or digital photography. Subjects who use traditional cameras will be permitted to enroll.

**Productive Engagement Groups.** (High-Demand and Moderate-Demand Photography) Sixty total participants will be assigned to one of the productive engagement groups (with thirty participants in each group): high-demand photography, and moderate-demand photography. Before the intervention begins, subjects will be provided equipment appropriate to their intervention for them to loan throughout the 12- to 14-week intervention. Participants in either of the photography groups will be supplied digital cameras. These 30 participants in each group may be separated further into smaller sections based on instructor availability in order to take advantage of smaller class sizes.

Each group will meet for 2.5 hours twice a week (5 hours per week total) at the research site. During this time, subjects will be stepped through a detailed curriculum by professional instructors, and those who learn techniques quickly will be pushed along so that maximum new learning occurs for each subject. Additionally, all subjects will be required to spend an additional 10 hours working on a special project at the research site without any formal instruction. This project is meant to provide participants with an opportunity to apply their skills to a task as they are learning. The high-demand photography group will learn similar skills as the moderate-demand photography group, but will learn them at a significantly quicker pace and, therefore, will learn more skills by the end of the intervention than the moderate-demand group.

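### The dose-response analysis ranks the at-home placebo on the same engagement scale as the two class arms, so a class-versus-home effect could be read as a dose-response to mental effort

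*Combined protocol and SAP*

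**What the plan says.** The protocol's Purpose section says the study should "determine whether mental effort is a contributing factor to changes in cognitive function". The Concise Summary states that "subjects will be randomly assigned to participate in one of 3 conditions with 30 subjects per group".

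Under Analyses of Secondary Outcomes, Dose-response, the SAP expects a single ordering, "with the control arms having the lowest values, high-engagement arms, the highest values, and moderate-engagement arms having values in between". It plans mixed models to size these effects and "to determine whether effects are linear or nonlinear in the degree of engagement". It gives no arm scores, no spacing, no term for setting and no rule for what would count as a dose-response. Neither the primary nor the secondary analysis text names a high-versus-moderate contrast.

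On the class arms, the Intervention section says "Each group will meet for 2.5 hours twice a week (5 hours per week total) at the research site", with professional instructors, plus 10 hours of project work on site. The two class arms differ in pace and in the number of skills reached. The placebo group, per the Concise Summary, "will engage alone at home in tasks that are relatively low in intellectual engagement". It has 5 required and 10 chosen hours a week and one weekly visit to the lab. Participant Recruitment, by contrast, calls it an "active placebo group that will engage in cognitively demanding activities at home".

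**The concern.** A dose-response analysis supports a claim about the dose only if the arms differ in nothing else that matters. Here the lowest level differs from the other two in several ways at once: home rather than research site, alone rather than in a group, no instructor, and no new skill. Any of these could affect memory without any role for mental effort. The protocol's own Background reports a cognitive benefit of social engagement in all five studies it found on that question.

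If the class package works but pace and demand add nothing, the true pattern is a step: moderate equals high, and both exceed placebo. A three-level trend can be significant under that pattern, and a small trial may not see that the shape is a step. The stake is the trial's central question. The Purpose section presents the study as a basis for a full trial, so a class effect attributed to effort could misdirect that trial.

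**Working it through.** **No figure to reproduce.** The SAP mentions sample-size calculations but shows none. It states no alpha, effect size, SD or baseline correlation.

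**Inputs from the documents.** Three arms of 30 ("We plan to enroll 90 participants in the Impact of Challenging Engagement study", so 90/3). Dropout is expected to be at most 15% to 20%. At 20%, 30 × 0.8 = 24 completers per arm.

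**Assumptions.** Two-sided 5% tests; equal arms scored 0, 1, 2; baseline-adjusted analysis; raw class-versus-home effect Δ of 0.2 to 0.8 SD; baseline–outcome correlation r of 0 to 0.8; no effort effect.

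**Set-up.** The residual SD after adjustment is √(1 − r²), so the effect in residual SD units is e = Δ/√(1 − r²). True means are placebo 0, moderate e, high e.

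- Linear contrast (−1, 0, 1): high minus placebo. Moderate has weight zero. Expected value e, SE √(2/n).
- Curvature contrast (1, −2, 1): expected value 0 − 2e + e = −e, SE √(6/n).
- High minus moderate: expected value 0, SE √(2/n).

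The linear and curvature contrasts are orthogonal, so the chance of a significant trend with no detected curvature is close to P(linear significant) × [1 − P(curvature significant)]. Power is from the noncentral t with 3(n − 1) − 1 degrees of freedom: 86 at n = 30, 68 at n = 24.

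**Worked case, Δ = 0.5, r = 0.6.** e = 0.5/0.8 = 0.625.

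| | n = 30 | n = 24 |
|---|---|---|
| Linear: e/SE | 0.625/0.258 = 2.42 | 0.625/0.289 = 2.17 |
| Linear trend significant | 67% | 57% |
| Curvature: e/SE | 0.625/0.447 = 1.40 | 0.625/0.500 = 1.25 |
| Curvature detected | 28% | 23% |
| Trend significant, no curvature detected | 0.668 × 0.718 = 48% | 0.569 × 0.766 = 44% |
| High versus moderate significant | 5% | 5% |

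Simulation agrees (48% and 43%). If the observed means must also fall in the order the SAP anticipates, the figures are 39% and 35%.

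**Range.** Chance of a significant trend with no detected curvature, 30 per arm, no effort effect:

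| r | Δ = 0.2 | Δ = 0.3 | Δ = 0.5 | Δ = 0.8 |
|---|---|---|---|---|
| 0 | 11% | 19% | 39% | 50% |
| 0.4 | 12% | 21% | 43% | 47% |
| 0.6 | 15% | 26% | 48% | 39% |
| 0.8 | 22% | 39% | 49% | 16% |

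The figure is low at one end because the trend itself is seldom significant. It falls at the other end because a large step is usually detected as curvature (84% at Δ = 0.8, r = 0.8).

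**Sensitivity of high versus moderate.** With the same degrees of freedom, 80% power needs a difference of 0.73 residual SD at 30 per arm and 0.82 at 24.

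**The case against.** The best defence is that the plan already looks for departures from linearity. A pure class effect is a step. It contradicts the expected in-between position of the moderate arm, and the nonlinearity check might catch it. A reader might infer that a class effect is bound to be reported as a dose-response. The documents do not support that, and even under my assumptions the misleading pattern appears in about half of trials at most. But the check is weak: in the worked case it detects the step in 28% of trials at 30 per arm. A detected step could also still be described as a plateau in engagement, because the model has no term for setting.

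A second defence is that the SAP does not fix a trend test. That stands. A reader might infer that the plan gives the moderate arm zero weight, but this is a property of the 0, 1, 2 scoring I assumed. What the documents show is an unspecified coding and no decision rule.

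Third, the SAP speaks of engagement, not effort, and the Purpose section does name a comparison of high with moderate demand, for brain changes. The primary model includes treatment arm, so that difference can be estimated. All true. But the SAP neither names the contrast nor ties the effort claim to it, so the choice is left until the data are seen.

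Finally, one might suppose that placebo also differs in weekly hours. It does not: the At-Home Engagement Group text gives 5 + 10 = 15, the same as the class arms.

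**Conclusion.** The concern holds as a risk of misinterpretation, not as proof that the analysis would mislead. The confounding of the lowest level follows from the documents alone. The size of the risk rests on assumed scores, effect sizes, correlations and a two-sided 5% level. Across the grid shown, between about one trial in nine and one in two would give a trend that looks like a dose-response when demand has no effect.

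This is a secondary analysis and does not affect the primary comparison. It should still be corrected, because it is the only place where the SAP comes near the trial's question about effort.

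The two descriptions of the placebo's cognitive demand, in the Concise Summary and in Participant Recruitment, conflict. That is a separate wording problem. It does not establish the confounding, but it leaves the placebo's place on the scale unclear.

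**What to change.** In the Dose-response paragraph of the SAP, prespecify two contrasts from the baseline-adjusted model:

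1. High-demand versus moderate-demand photography, as the test of mental effort.
2. The mean of the two photography arms versus placebo, as the effect of the whole class package (setting, instruction, peers, new skill and effort together).

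Add that a dose-response to mental effort will be claimed only if contrast 1 supports it. The three-arm linear or nonlinear model may remain as description, with its arm scores stated. Reconcile the two protocol descriptions of the placebo activities.

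The change costs SAP wording only: no new data, visits or participants. The price is that the effort claim becomes harder to reach, given the detectable differences shown in the working. With r = 0.6 these equal 0.73 × 0.8 = 0.58 and 0.82 × 0.8 = 0.66 raw SD. That limit comes from the design and is better stated in the SAP, so that a non-significant contrast 1 is not read as evidence of no effort effect.

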## Statistical Analysis Plan

Preliminary Analyses. In initial analyses, we will summarize categorical variables by proportions and continuous variables by means and quantiles. We will graph continuous variables and assess them for skewness, transforming if necessary (for example by logs or square roots) to render them more nearly normally distributed. We will explore relationships among variables by examining scatter plots and correlation matrices. We will conduct all analyses in R (version 3.3.2 or later) or SAS (version 9.4 or later).

Analysis of Primary Outcome Variables. The primary cognitive outcome endpoint will be a composite, scalar episodic memory score, as described in earlier research from the SYNAPSE project (5). This measure will exhibit substantial between-subject variability, in that subjects who give high scores at baseline are likely to give high scores at follow-up as well. To account for this, in primary analyses we will adjust for baseline levels by analysis of covariance — i.e., including baseline values together with treatment arm in a regression model for the post-treatment outcome. Alternatively (and equivalently), we can analyze the outcome variable in a mixed model, evaluating a treatment effect by estimating a time-by-treatment interaction. We will moreover conduct mixed-model analyses including the intermediate (6-week, mid-treatment) and long-term (1-year) values of the cognitive outcomes together with the end-of-treatment (12-week) outcome. As a secondary analysis to further elucidate the magnitude and timing of treatment effects, we will seek to create parsimonious models of this outcome as a function of time, treatment arm, stratification factors (center, age, sex, education) and potentially other factors measured at baseline. The primary brain outcome will be a vector measure of fMRI activation in four brain regions of interest, as described above and in previous work from SYNAPSE (7). This measure is also likely to exhibit substantial between-subject variability. We will again analyze the outcome variable in a mixed model, evaluating the treatment effect by estimating a time-by-treatment interaction, and conduct a secondary analysis where we model activation in the four regions as functions of time, treatment arm, stratification factors (center, age, sex, education) and potentially other factors measured at baseline.

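### The SAP calls age and center stratification factors, but the described assignment names neither, so balance on them is not ensured; as a minor point, two subgroup cut-points are left unplaced

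*Combined protocol and SAP*

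**What the plan says.** In the Statistical Analysis Plan, under the primary outcome variables, the secondary models for both the memory composite and the fMRI measure use time, arm and "stratification factors (center, age, sex, education) and potentially other factors measured at baseline". The primary memory analysis is a covariance model with the baseline score and treatment arm. Its alternative is a mixed model with a time-by-treatment term.

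The protocol section on the Intervention (Weeks 3-16) says that subjects are "pseudo-randomly assigned to intervention groups (based on gender and education criteria and the needs of the study"). The Concise Summary of Project says only that assignment to three groups of 30 is random and names no factor.

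The SAP's Subgroup Analyses paragraph defines "strata of age (younger or older than age 72), gender (male or female), education (greater or less than 14 years") and adds center, with Dallas and Hamburg as its levels. It continues: "We expect each of these strata to comprise roughly half of the subjects, except that our sample will likely be 65% female". It then commits to use the strata: "We will replicate our main analyses in each of the stratum subgroups, and additionally test for interactions".

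**The concern.** A stratification factor is a property of the design: the arms were made similar on it at assignment. A reader of the SAP would conclude that this was done for age and center, and the assignment text does not support that. Age matters here because entry spans 60 to 90 years, the outcome is memory, and the SAP itself picks age as a subgroup factor. If age balance is left to chance in arms of 30, the primary model has no age term to correct a chance imbalance, and the age term in the secondary models rests on a description that the design does not match. Center has the same problem: no assignment text mentions it.

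Separately, the age and education strata are written with strict inequalities on both sides. Someone aged exactly 72, or with exactly 14 years of schooling, is eligible but has no stated stratum. The analyst would have to choose a side, possibly after seeing data.

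**Working it through.** **Factors side by side**

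| Factor | SAP stratification list | Protocol assignment text |
|---|---|---|
| Sex/gender | yes | yes |
| Education | yes | yes, no cut-point given |
| Age | yes | not named |
| Center | yes | not named |
| Study needs | no | yes, undefined |

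Two of the four SAP factors are matched. The documents give no allocation list, block scheme or minimisation rule that could settle the other two.

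**Chance imbalance in mean age.** The input from the protocol is three arms of 30. The assumption is that age plays no part in assignment. The standard error of an arm's mean age is 1/√30 = 0.183 SD. A gap of 0.3 SD between the highest and lowest arm is 0.3/0.183 = 1.64 standard errors, and a gap of 0.5 SD is 2.74. Simulating three arm means 200,000 times gives:
- P(range > 0.3 SD) = 0.476
- P(range > 0.5 SD) = 0.128

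**Chance imbalance in the older share.** Take 45 of 90 as older, in line with the SAP's expectation of rough halves. A difference of 20 percentage points is 6 people out of 30.
- Two given arms (hypergeometric): P(difference ≥ 6) = 0.157
- Largest gap among three arms (50,000 permutations): P(≥ 6) = 0.324

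**What an imbalance does.** Let r be the correlation between age and the outcome that remains after adjustment for the baseline score. An age gap of g SD between two arms then shifts their contrast by about r × g residual SDs. The documents give no value for r, so the shift cannot be sized. It is zero only if the baseline score already carries all of age's effect.

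**Cut-points.** Age 72 lies within 60 to 90, and 14 years lies above the 10th-grade minimum. The documents give no distribution for either, so the counts below are illustrations only.
- Age: an assumed 2% to 5% at exactly 72 gives 90 × 0.02 = 1.8 to 90 × 0.05 = 4.5 people. Whole-year ages spread evenly over 60 to 90 give 90/31 = 2.9. That even spread does not fit the SAP well: it puts 12/31 = 39% below 72 and 18/31 = 58% above, not about half each.
- Education: an assumed 5% to 20% at exactly 14 years gives 90 × 0.05 = 4.5 to 90 × 0.20 = 18 people, or 1.5 to 6 per arm.
- With each boundary value placed on one side, the number without a stratum is zero.

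**The case against.** A reader might infer that assignment uses gender and education and nothing else. The text does not say so: the undefined third criterion could include age. What stands is narrower: an undefined criterion is not a stated stratification factor.

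A reader might also infer that age is unbalanced. That is not shown. Any random element balances age in expectation, and the 48% and 13% are ordinary chance figures for any unstratified baseline variable in three arms of 30. Comparisons within age strata are valid without stratified assignment, and the baseline memory score in the primary model absorbs part of age's effect. All of this is right. The point that remains is that the SAP labels as secured something that the described assignment leaves to chance, while the primary model has no age term.

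Age does already enter the secondary models, so part of the remedy exists. The form of the age term is not specified, however, and it is absent from the primary analysis.

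On the cut-points, a reader might infer that the subgroup analyses will lose a material number of people. The expectation of rough halves shows that a split of the whole sample is intended, and an analyst would probably close the gap sensibly. Date of birth is collected, and with exact age almost nobody is exactly 72. The interaction tests may not use the dichotomised factors at all. What is left is loose wording, worth fixing because fixing it costs nothing.

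**Conclusion.** The mismatch is real. The SAP describes stratification on four factors, and the protocol's assignment text supports two of them. Balance on age and on center is not ensured by design, although age balance holds in expectation under random allocation. If age plays no part in assignment, a range of arm mean ages above 0.3 SD has a chance of about 48%, and above 0.5 SD about 13%. These figures measure the exposure to chance that the stratification label would lead a reader to think had been reduced. They are not evidence of bias in this trial, and the effect on a treatment contrast cannot be computed from the documents.

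The primary analysis remains valid as written. The case for change is protection against chance imbalance, possibly better precision, and an SAP that describes the design correctly. The boundary gap at 72 years and 14 years is minor: it concerns secondary subgroup analyses only, and its size is unknown.

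**What to change.** Make the SAP list and the assignment text agree, and define or delete the open study-needs criterion.

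- **If assignment is still open:** add age to the assignment factors, for example by minimisation. If education is split in two (the protocol gives no cut), age takes the cells from 4 to 8. That averages 90/8 = 11 people per cell, or under 4 per arm, and the male cells are smaller at 35% men. This is why minimisation suits better than many small blocks. Treat center the same way if there is more than one; otherwise delete it.
- **If assignment is done:** remove age and any other unused factor, such as center, from the stratification factors. Enter age as a continuous covariate in the between-arm models, including the primary covariance analysis, and fix this before outcomes are examined. Where the treatment effect is a time-by-treatment term, as in the mixed models, include age-by-time as well, because age alone does not adjust a change contrast. The cost is one degree of freedom: with intercept, two arm terms and baseline, 90 − 4 = 86 residual degrees of freedom become 85.
- **Subgroup paragraph:** place each boundary value, for example <72 versus ≥72 years and <14 versus ≥14 years of education, and state whether age is exact or in completed years. Use the same education cut in the assignment rule.

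Age is already known at screening, so nothing new is collected. The work is a few lines of text and, at most, one more assignment factor.

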### **Criteria for the Inclusion of Participants.**

- Participants must be adults between 60 and 90 years old.
- At least 35% of participants will be men, and at least 15% will be minorities.
- 10th grade education or higher is required
- Fluent in English
- ADAS-COG score of zero (a perfect score).
- A score of 18 or higher on the Barthel Index of Daily Functioning.
- Right-handed for MRI scanning.

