### **Basic Information (Including Education)**

Self-developed

- Participants are asked for basic demographic information.
- This questionnaire has 39 questions concerning:
  - Live Alone/Housing Status
  - Marital Status
  - Education
  - Date of Birth
  - Gender
  - Occupation
  - Native Language/Bilingualism
  - Birth Country

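### Age and education moderation is planned through two-level strata, with no continuous interaction term specified and no rule that the interaction test outranks within-stratum results

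*Combined protocol and SAP*

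**What the plan says.** The Subgroup Analyses paragraph of the SAP defines its subgroups as "strata of age (younger or older than age 72), gender (male or female), education (greater or less than 14 years". A fourth factor is the study site, with Dallas and Hamburg as its two levels. On their size, the paragraph says "We expect each of these strata to comprise roughly half of the subjects", with an exception for sex, where about 65% women are expected. The method is one sentence: "We will replicate our main analyses in each of the stratum subgroups, and additionally test for interactions".

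The SAP's section on primary outcome variables separately plans secondary whole-sample models in which center, age, sex and education may enter as predictors. It does not say whether age and education are continuous or categorical there, and it names no product term with arm.

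The protocol allocates participants to "one of 3 conditions with 30 subjects per group". The inclusion criteria state "Participants must be adults between 60 and 90 years old". The Incomplete data paragraph says "we expect no more than 15% to 20% of subjects to fail to complete the followup evaluation schedule". In Appendix A, the Basic Information questionnaire ("Participants are asked for basic demographic information") lists date of birth and education among its items.

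**The concern.** Two separate weaknesses sit in the one method sentence.

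First, the only age and education variables that the paragraph defines are two-level. An interaction test built on them treats a 61-year-old and a 71-year-old as identical, so it is less able to detect a gradual change in benefit with age or education.

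Second, the main analyses are repeated in strata of roughly 15 per arm, with no multiplicity rule and no statement of which result governs. Significance in one half and not in the other is not evidence that the halves differ, yet the plan does not rule out that reading.

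The protocol presents this study as groundwork for a full trial. A missed or spurious age or education gradient could misdirect that trial's eligibility or stratification.

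**Working it through.** The documents give no power, effect size or error rate for the subgroup analyses, so there is no stated figure to reproduce. The following are assumptions: two-sided 5% tests, a linear gradient, the shape of the age distribution, and (in simulations) a baseline-to-outcome correlation of 0.7.

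**1. Information kept after a split.** The relative efficiency of a split moderator is the squared correlation between the variable X and the indicator that X exceeds the cut.
- Uniform, with a share p above the cut: 3p(1−p). For ages uniform on 60–90, p = 18/30 = 0.6, which gives 3 × 0.6 × 0.4 = 0.72. If 72 is the median (for example uniform on 60–84), 3 × 0.5 × 0.5 = 0.75.
- Normal, cut at the median: 2/π = 0.637.
- Normal truncated to 60–90, mean 68 to 74, SD 5 to 9, cut at 72: 0.56 to 0.69.

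The split therefore keeps 56% to 75% and loses 25% to 44%. A 15% to 20% loss from 90 leaves 76.5 to 72, say 75 completers. They would test a linear age gradient like 75 × 0.56 = 42 to 75 × 0.75 = 56 people.

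**2. Effect on power.** If the continuous interaction has 80% power, its expected z is 1.960 + 0.842 = 2.802.
- Efficiency 0.637: Φ(2.802 × √0.637 − 1.960) = Φ(0.276) = 61%.
- Efficiency 0.75: Φ(2.802 × √0.75 − 1.960) = Φ(0.466) = 68%.

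Simulations with 75 completers, for age moderation of high-demand against placebo, used assumed slopes of 0.4 and 0.6 per SD of age. Power fell from 37–44% to 27–31% for the smaller slope, and from 70–74% to 51–56% for the larger.

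**3. Education.** Its distribution is not given. Three assumed distributions over 12 to 18 years gave a loss of 6% to 35% for a cut at 14. This is illustrative only.

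**4. Size of the strata.** Thirty per arm, halved, is 15. After 15% to 20% loss it is 12.75 to 12. For men at 35%: 10.5 per arm, or 8.9 to 8.4 after loss. The imaging outcome has fewer, because scanning is optional and needs further eligibility.

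The standardized difference detectable with 80% power is 2.802 × √(2/n): 0.72 at n = 30, 1.02 at 15 and 1.14 at 12. A difference of 0.723 has power Φ(0.723/√(2/15) − 1.960) = Φ(0.021) = 51% in each half. With the same true effect in both halves, the chance that exactly one is significant is 2 × 0.51 × 0.49 = 50%.

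**5. Chance findings with no effect.** Analysis of covariance was repeated in the six age, education and sex strata (3,000 to 4,000 simulated trials per run, 75 or 90 participants).
- One overall arm test per stratum: at least one p<0.05 in 21–22% of trials.
- Three arm contrasts per stratum (18 tests): 44–45% of trials, with about 0.9 false positives on average.
- Adding center (eight strata, one overall test each): 27%.
- Two interaction tests, for age and education: 9%, whether the moderators are split or continuous.

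**The case against.** The SAP does plan interaction tests, which are the standard safeguard against over-reading one half, and it plans whole-sample models that include age and education. A reader might infer that moderation is examined only by splitting and repeating. The documents do not support that. The coding of the interaction terms is unstated, and if they are continuous the information loss disappears. What stands is that the paragraph defines no variable other than the strata, and that the whole-sample models name no arm-by-covariate term.

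A reader might also infer that repeating the analyses discards information, or that splitting causes the chance findings. Neither follows. The loss comes from dichotomising, and the chance findings come from many uncontrolled within-stratum tests. Split and continuous interaction tests gave the same 9%.

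Nor can a loss of about a third be claimed for education, or 45% be quoted alone. The SAP does not say that three contrasts will be run in each stratum.

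Finally, the paragraph describes its aim as estimation, and no text says a claim will rest on one half. Under the assumed slopes, even the continuous test has less than 80% power. Both points limit how much is gained, but neither is a reason to keep the weaker test or leave precedence open.

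**Conclusion.** The point holds as a gap in specification with a better method available. On the natural reading, the interaction tests use age and education cut in two. For age this costs about 25% to 44% of the information on a linear gradient; for education the cost cannot be fixed from the documents. Within-stratum testing without a precedence or multiplicity rule gives at least one chance finding in about 21% to 45% of null trials across six strata.

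These figures rest on the assumed distributions, linearity, 5% tests and the number of contrasts per stratum. The analyses are secondary and the primary comparison is unaffected. The change is worth making, but it is not critical.

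**What to change.** Amend the Subgroup Analyses paragraph as follows.
- In the full sample, test arm-by-age and arm-by-years-of-education with both as continuous variables, and test arm-by-sex. Keep arm-by-center if a second center takes part. Check linearity with a quadratic term.
- Report arm effects at chosen ages and education levels, and by sex, with 95% confidence intervals from these models.
- Keep the within-stratum results as descriptive estimates with confidence intervals and no p-values.
- State that any claim of a subgroup difference rests on the interaction test.

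The cost is SAP wording. Date of birth and education are already collected; confirm that education is recorded in years. The downside is the linearity assumption, which the quadratic term can check only roughly at this sample size.
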